### 9.1. Use of analysis populations in different analyses

Analyses	Safety population/ Intent to Treat Population	Modified Intent to Treat Population	Efficacy Evaluable Population	Per Protocol Population
Baseline Assessments (including demographics, disease characteristics, prior therapies)	✓		✓	
Compliance and exposure	✓	✓	✓	✓
PD Assessments		✓	✓	
Efficacy: Primary endpoint			✓	✓
Efficacy: Secondary endpoints			✓	✓
Safety (including concomitant therapies)	✓			

## 10. GENERAL ISSUES FOR STATISTICAL ANALYSIS

### 10.1. Definition of Treatment Arms

It is a single-arm study, all subjects will receive the same IMP, BIM23B065. Patients with the different dosing regimens (BID and TID) will be presented as “BID” and “TID” subjects.

### 10.2. Definition of Baseline

Most baseline assessments will be performed on Day -1 (Visit 3) with some exceptions. In case the data of the planned baseline assessment is not available, the last assessment which precedes the first administration of the IMP will be used as a baseline.

*Statistical Analysis Plan*

*SD-BS-014, version 1.0*

*Parent document: SOP-BS-005*

**Protocol code:** D-FR-10380-002

**Protocol Title:** A phase IIA, open-label, single-arm, two stage, multi-centre study to investigate the pharmacodynamics, pharmacokinetics, safety and tolerability of repeated subcutaneous administration of BIM23B065 in subjects with acromegaly

- For the GH and PRL calculations the mean serum concentration will be used as baseline, collected over 6 hours on the Day -1. The baseline IGF-1 will be measured on Day -1.
- For antibodies anti-BIM23B065 the baseline will be the serum concentration taken prior to octreotide test dose, on V2.
- For other laboratory assessments (all endocrine and clinical laboratory assessments, parameters of glucose metabolism etc.) baseline will be the measurement of Day -1. At the parameters of glucose metabolism more baseline values will be used in accordance to the fasting condition or the relative time from meals (the fasting condition on Day -1 will be compared with the fasting condition of the studied day, while the assessment one hour after meal will be compared to the baseline (Day -1) one hour after meal measurement etc.).
- For BP and HR, orthostatic hypotonia, and ECG, the baseline will be the corresponding measurements on Day -1 at the same time points (i.e. time-matched). For Holter the baseline will be the assessment on Day -1.
- For gallbladder echography, the baseline will be the assessment during the screening period.
- For other results of the physical examination (body weight, body temperature etc.) the D-1 assessments will be the baseline.

### **10.3. Definition of Visit Windows**

There will be two stages. During Stage 1, the subjects will be enrolled to receive BIM23B065 BID, and during Stage 2, TID.

Both the BID and TID regimen parts will consist of 3 periods: screening, treatment, and follow up.

Screening period will start on the date of signing the informed consent and ends on the Day -1, the day preceding the first dose of IMP on Day 1. Treatment phase will start on Day 1 and ends with the Visit 8. Follow up phase starts on the following day of the Visit 8 and ends with the End of Study/Early Discontinuation visit.

Throughout the study 9 visits are planned (please see Study Schedule of Events in the Protocol). During the analysis visits will not be re-defined, eCRF visits will be used. Visits will be presented with the following labels: SCR (screening) D-1 (first day of Visit 3, pre-dose day), D1 – D14 (Day 1 is the first dosing day), EOS (End of Study day), ED (Early Discontinuation).

### **10.4. Multicentre Study**

This is a multicentre study planned to be conducted in multiple centres from approximately 6 countries. No subgroup analyses are planned by country, the data of the sites will be pooled.

*Statistical Analysis Plan*

*SD-BS-014, version 1.0*

*Parent document: SOP-BS-005*

**Protocol code:** D-FR-10380-002

**Protocol Title:** A phase IIA, open-label, single-arm, two stage, multi-centre study to investigate the pharmacodynamics, pharmacokinetics, safety and tolerability of repeated subcutaneous administration of BIM23B065 in subjects with acromegaly

### 10.5. Planned Subgroup Analyses

Two age categories will be defined: subjects with 18-64 years age at baseline, and subjects with 65-75 years age at baseline. Descriptive statistics for the disposition, demographics, baseline characteristics, AE, primary and secondary endpoints will be prepared by age category and by octreotide responder category (responders/non responders).

### 10.6. Analysis Software

All analysis will be performed using SAS® Software version 9.3 or above.

### 10.7. Derived and Computed Variables

The following derived and computed variables have been initially identified. It is expected that additional variables could be required. The SAP will not be amended for additional variables unless they are directly related to the primary endpoint or key secondary efficacy variables. Any additional derived or computed variables will be identified and documented in the ADaM requirement documentation and/or in the footnotes of the outputs, where appropriate.

Variable Name	Description	Valid values (Ranges)	Computation methods, Notes or equation(s)
OTPDMEN	Mean GH over 6 hours after octreotide dosing during Octreotide Test	0-200 ug/L	= [SUM(GH measurements 1, 2, 3, 4, 5, 6 hours post octreotide dose)]/number of valid GH measurements
OTRBL	Reduction from Baseline in GH level during Octreotide Test	0-100 %	= [1- (OTPDMEN/ Baseline GH level)] x 100
GHMDX	Mean GH over 6 hours measured on DayX	0-200ug/L	= [SUM(GH measurements 1, 2, 3, 4, 5, 6)]/number of valid GH measurements over 6 hours on DayX]

Protocol code: D-FR-10380-002

Protocol Title: A phase IIA, open-label, single-arm, two stage, multi-centre study to investigate the pharmacodynamics, pharmacokinetics, safety and tolerability of repeated subcutaneous administration of BIM23B065 in subjects with acromegaly

Variable Name	Description	Valid values (Ranges)	Computation methods, Notes or equation(s)
GHRGL	Reduction from Baseline in GH level on DayX	0-100 %	= [1- (GHMDX/GHM(D-1))] x 100

As a general rule mean will be calculated by summarizing the available valid (non-missing) measurements and divided by the number of measurements. Percent change from baseline will be calculated according to the following:  $[1 - (\text{present value}/\text{baseline value})] \times 100$ .

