### 12.4.2. Baseline Octreotide Test

Number and percentage of enrolled octreotide responders and non-responders will be presented.

All enrolled subjects will be listed along with their octreotide test results. The baseline GH level, the mean GH in the 6 hours after a single sub-cutaneous injection of 100ug octreotide, the reduction from baseline (in %) and the responder status will be presented. An octreotide responder is defined as having a >50% reduction from baseline in mean GH in the 6 hours.

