### **13.2.1. GH responders**

The following secondary GH response criteria will be defined on Day 7 and Day 14 based on the GH profiles:

- Mean GH  $\leq$  1.0 ug/l
- Mean GH  $\leq$  2.5 ug/l
- Mean GH reduction from baseline  $\geq$  50%

The GH measurements, their mean by visit, the mean percent changes from baseline and the various GH responder criteria will be listed by patient and visit. The number and proportion (90% CI calculated by the Clopper-Pearson method) of GH responders on Day 7 and Day14 will be reported.

Descriptive summaries will be presented for the measured GH values and for the calculated percent changes from baseline. Mean (+ SE) profiles over time will be displayed graphically.

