### **13.2.2. PD endpoints**

The IGF-1 and PRL measurements and the mean of the PRL concentration will be listed by patients and by visits along their change from baseline in percent.

Descriptive summaries will be presented for the measured concentration values and for the calculated percent change from baseline in the mITT set. Mean (+ SE) profiles over time will be displayed graphically.

The number and proportion (%) of subjects with IGF-1 < age normalized ULN, will be presented by visit along with the 90% Clopper-Pearson CI.

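### SAP Section 10.7 gives the name percent change to a percent-reduction formula, so falls in GH, IGF-1 and PRL are reported as positive; the stated range for the two reduction variables also contradicts that formula

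*SAP*

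**What the plan says.** Three parts of the SAP bear on this.

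- **General rule, Section 10.7.** The text below the table of derived variables says "Percent change from baseline will be calculated according to the following", followed by (1 - P/B) x 100, where P is the present value and B the baseline value.
- **Table in Section 10.7.** The same expression defines OTRBL, for the octreotide test, and GHRGL, described as "Reduction from Baseline in GH level on DayX". Both have a valid range of 0 to 100%. The Day X GH mean, GHMDX, has a valid range of 0 to 200 ug/L.
- **Outputs.** Some places use the word reduction. For the octreotide test, Section 12.4.2 says "the reduction from baseline (in %) and the responder status will be presented". In Section 13.2.1 the 50% response criterion is headed "Mean GH reduction from baseline". Other places use percent change. The GH listing in Section 13.2.1 says "the mean percent changes from baseline and the various GH responder criteria will be listed by patient and visit", and the GH summary there reads "Descriptive summaries will be presented for the measured GH values and for the calculated percent changes from baseline". For IGF-1 and PRL, Section 13.2.2 lists measurements "along their change from baseline in percent" and provides summaries "for the calculated percent change from baseline in the mITT set".

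The SAP has no other formula for percent change, and no statement that a positive percent change denotes a fall.

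**The concern.** Reduction and change ordinarily carry opposite signs, yet Section 10.7 gives both names to one expression. A programmer who follows the rule produces GH, IGF-1 and PRL listings and summaries whose signs are reversed relative to their label. A drug that lowers GH would show a positive mean percent change, and a subject whose GH doubles would show -100%, a figure normally read as suppression to zero. Section 3.3 intends the planned analyses for regulatory submissions and/or manuscripts, where readers will see the label and may not have the formula.

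The range is a separate, smaller defect in the same table. A valid range that the variable's own formula can leave is a wrong specification.

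**Working it through.** **Inputs.** The formula, the variable names and the ranges come from SAP Section 10.7. The baseline of 10 ug/L and the present values below are illustrative assumptions, not figures from the SAP.

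**Step 1: sign.** With P the present value and B > 0 the baseline value:

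- as written: (1 - P/B) x 100
- ordinary percent change: [(P - B)/B] x 100 = (P/B - 1) x 100

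The first is minus the second at every value. They agree only when P = B, where both are zero.

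**Step 2: numbers, with B = 10.**

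| Present value P | As written | Ordinary percent change | Within 0 to 100% as written? |
|---|---|---|---|
| 4 | (1 - 0.4) x 100 = +60% | -60% | yes |
| 5 | (1 - 0.5) x 100 = +50% | -50% | yes |
| 10 | (1 - 1) x 100 = 0% | 0% | yes |
| 12 | (1 - 1.2) x 100 = -20% | +20% | no |
| 20 | (1 - 2) x 100 = -100% | +100% | no |

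The second row is a subject exactly at a 50% reduction, who would be listed with a percent change of +50%.

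**Step 3: range.** For P at or above 0 and B > 0, the formula has a maximum of 100% (at P = 0) and no lower bound. It is negative whenever P exceeds B. The table lets GHMDX lie anywhere from 0 to 200 ug/L and does not tie it to the Day -1 mean. A Day -1 mean of 10 and a Day 14 mean of 12 are therefore both valid, yet GHRGL is -20%, outside its stated range. OTRBL has the same form and the same problem. Only the upper limit of 100% agrees with the formula.

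**Step 4: does any decision depend on it?** A reduction of at least 50% means P/B is at most 0.5. That is the same as (1 - P/B) x 100 being at least 50, or the ordinary percent change being at most -50. All three select the same subjects. The criteria are written as reductions and the variables that carry them are named as reductions, so responder classification does not change. The tests, interim counts and sample size that rest on it do not change either.

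**The case against.** The strongest reply is that nothing is undefined. The formula is printed, every programmer will get the same number, and its direction suits a trial whose aim is to lower GH. The affected outputs are descriptive, and the measured values are listed and summarised in the same sections, so the direction can always be checked. All of this is true, and it keeps the point minor. It does not remove it. The output carries the label, not the formula, and Section 10.7 already has the right name for the expression. The footnote provision in that section covers additional variables and does not promise a note on sign.

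Four stronger readings are tempting, and the SAP does not support them.

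- **Responders would be misclassified.** They would not; see the last step of the check.
- **Rises in GH would be dropped or set to zero because they fall outside 0 to 100%.** The SAP states no such rule. Section 10.7 uses valid to mean non-missing when it describes means, and the missing-data section specifies observed cases without substitution.
- **The places allowed for octreotide non-responders show how often the range would be breached.** They do not. A non-responder may have any reduction up to 50%, which is within the range. Any entry limit on the test result belongs to the eligibility criteria, which the SAP leaves to the protocol.
- **The GH listing contradicts itself by showing one number under two names.** The text does not say that a separate reduction column appears; the criteria may be shown only as met or not met. Under the SAP's own convention, +50% has the same sign as the 50% reduction criterion. The conflict is with the ordinary meaning of percent change.

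**Conclusion.** The point holds as a minor reporting error. Under the rule as written, every non-zero GH, IGF-1 and PRL value labelled percent change has the opposite sign to the ordinary one, with the same absolute size. The octreotide listing is already labelled a reduction, so the label error does not touch it.

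The range of 0 to 100% for OTRBL and GHRGL is wrong on the table's own terms, but no effect on an output has been shown. How many subjects will show a rise cannot be known from the SAP.

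The conclusion assumes that the general rule in Section 10.7 governs the percent-change outputs in Sections 13.2.1 and 13.2.2. No other rule is given. The SAP does not say whether the graphical profiles in those sections plot measured values or percent changes, so no claim is made about the figures.

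**What to change.** In Section 10.7, choose one of two routes and apply it to all the GH, IGF-1 and PRL listings and summaries in Sections 13.2.1 and 13.2.2:

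1. define percent change from baseline as [(present value - baseline value)/baseline value] x 100; or
2. keep the existing expression and rename these outputs percent reduction from baseline.

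On either route, keep (1 - present/baseline) x 100 under the name percent reduction for the 50% GH criterion and the octreotide test. Restate the valid range of OTRBL and GHRGL as at most 100%, with negative values kept as observed.

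The cost is a few lines of SAP wording. It needs no additional subjects or data and does not change the primary analysis.

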#### 10.1. Methods for Missing Data

A subject is considered evaluable if he or she completes the 14-day treatment period (with 6 hours GH samples collected). Subjects who withdraw from the study before reaching the point of being evaluable may be replaced. If the withdrawal is due to safety and tolerability reasons no replacement will be performed, but otherwise the subject will be replaced. If 12 evaluable subjects have already completed visit 8 (day 14) any subsequent withdrawn subjects will not be replaced.

A minimum of 8 octreotide responders must be evaluable in the final analysis. If an octreotide responder withdraws prematurely, he/she will be replaced by another octreotide responder. If an octreotide non-responder withdraws, they can be replaced by either a responder or non-responder.

No substitution of missing values will be performed, an observed case approach will be used.

In all listings, missing or incomplete dates will be left as they have been recorded. However, for calculation / sorting / assignation based on dates, the following methods will be used:

- The most conservative approach will be systematically considered. For example, if the onset date of an AE/concomitant medication is missing / incomplete, it is assumed to have occurred during the study treatment phase (i.e. a TEAE for AEs) except if the partial onset date or other data (e.g. stop date) indicates differently.
- A missing/incomplete date of medical history or disease diagnosis will be assumed to have occurred before any study treatment.

Where this is possible, the derivations based on a partial date will be presented as superior inequalities (i.e.: for an AE started in FEB2004 after the administration performed on

**Protocol code:** D-FR-10380-002

**Protocol Title:** A phase IIA, open-label, single-arm, two stage, multi-centre study to investigate the pharmacodynamics, pharmacokinetics, safety and tolerability of repeated subcutaneous administration of BIM23B065 in subjects with acromegaly

31JAN2004, the days since last dose will be “≥2”, similarly the duration of ongoing AEs or medication will be “≥xx” according to the start and last visit dates).

If the severity or the relationship to the IMP is not available for an AE it will be marked as ‘unknown’.

## **11. STUDY SUBJECTS**

Information on subjects of Stage BID and Stage TID will be presented in separately in lists and in the same tables.

### **11.1. Disposition of Subjects and Withdrawals**

Disposition data will be listed for all subjects who entered this study.

A frequency table will be created displaying disposition of patients including:

- Total number of subjects entered (subjects who gave informed consent);
- Number of screening failures/withdrawals before enrolment
- Number of enrolled subjects
- Number of subjects in the ITT set (subjects who received at least one IMP administration);
- Number of subjects withdrawn after the treatment start date;
- Number of subjects completed the treatment phase;
- Number of subjects completing the study (including follow up);

Withdrawals/Discontinuations during the treatment period will be summarized by the coded term for main reason of withdrawal (patients with a reason recorded as “other” will have an own category). Subjects withdrawn will be listed along with the reason and date of discontinuation.

### **11.2. Protocol Deviations**

Protocol deviations will be assessed from medical aspect during a data review meeting before database lock in order to decide on subject’s eligibility to PP, EE and mITT populations. Protocol deviations will be classified as either minor or major. Details of protocol deviation evaluation will be provided in the study specific Protocol Deviation Handling Plan.

Protocol deviations per subjects will be listed along with the description of the deviation and ‘minor’ or ‘major’ evaluation flags.

*Statistical Analysis Plan*

*SD-BS-014, version 1.0*

*Parent document: SOP-BS-005*

**Protocol code:** D-FR-10380-002

**Protocol Title:** A phase IIA, open-label, single-arm, two stage, multi-centre study to investigate the pharmacodynamics, pharmacokinetics, safety and tolerability of repeated subcutaneous administration of BIM23B065 in subjects with acromegaly

### **11.3. Study Participant Disposition**

The numbers and percentages of enrolled subjects included in the ITT, mITT, EE and PP populations will be tabulated. The reasons for subject exclusions from the populations will also be listed.

## **12. DEMOGRAPHICS AND OTHER BASELINE CHARACTERISTICS**

### **12.1. Demographics**

Demographics will be presented descriptively for the ITT set.

Descriptive statistics for continuous variable (age at baseline in years) will comprise N, arithmetic mean, standard deviation, minimum value, median, maximum value and number of non-missing values. Age (in integer, years) will be calculated from the difference between the recorded exact or rounded date of birth and the date of informed consent.

Descriptive statistics for categorical variables (gender, race, ethnicity, age category) will comprise numbers of subjects and percentages in each category.

### **12.2. Drug Exposure**

Incidence tables will present the actual doses per day. The descriptive statistics of the final and cumulative doses at the end of the titration and treatment periods will be presented. Total daily doses will be summarized and tabulated by day.

The administered and planned total daily doses of each day will be listed with the cumulative doses at the end of the titration and treatment periods.

Exposure time being the number of days when the subject received IMP will be summarized.

### **12.3. Prior and Concomitant Medications**

Prior/concomitant medications will be coded using WHO Drug Dictionary (June 2016 Version or higher). These therapeutics will be listed by subject and by the second level of Anatomical Therapeutic Chemical (ATC) classification system code and ATC4 terms. Prior medication is defined as medication with a start date prior to the date of the first administration of the study medication.

**Protocol code:** D-FR-10380-002

**Protocol Title:** A phase IIA, open-label, single-arm, two stage, multi-centre study to investigate the pharmacodynamics, pharmacokinetics, safety and tolerability of repeated subcutaneous administration of BIM23B065 in subjects with acromegaly

## 12.4. Baseline and Screening Conditions

Ideally, in general, baseline control assessments will be performed on Day -1 (Visit 3), for detailed description please see Section 10.2.

### 12.4.1. Baseline Medical History

Medical history/current medical condition events will be coded using MedDRA 19.1 or higher. These events will be listed by subject and by system organ class (SOC) and preferred terms (PT).

The history of acromegaly will be detailed. Subjects will be listed with the date of acromegaly diagnosis, disease duration, the number of pituitary surgeries, the date, time since and the type of the last surgery and whether the patient is treatment naïve or not. Descriptive summaries will be presented for the main acromegaly characteristics.

### 12.4.2. Baseline Octreotide Test

Number and percentage of enrolled octreotide responders and non-responders will be presented.

All enrolled subjects will be listed along with their octreotide test results. The baseline GH level, the mean GH in the 6 hours after a single sub-cutaneous injection of 100ug octreotide, the reduction from baseline (in %) and the responder status will be presented. An octreotide responder is defined as having a >50% reduction from baseline in mean GH in the 6 hours.

### 12.4.3. Baseline Body Temperature, Height and Weight

Descriptive statistics for baseline vital signs (body weight, body height, body temperature along with the location of the measurement and D1 (predose) will be presented and the results will be listed.

## 12.5. Measurement of Treatment Compliance

Compliance factor will be determined for BIM23B065 on each day according to the following equation:

$$\text{Compliance (\% (on a day))} = \frac{\text{Amount of BIM23B065 Administered}}{\text{Amount of BIM23B065 Expected to be Administered}} \times 100$$

$$\text{Overall compliance (\%)} = \frac{\text{Cumulative administered BIM23B065}}{\text{Cumulative BIM23B065 Expected to be Administered}} \times 100$$

A subject will be considered as compliant on a day if its compliance rate is between 80 and 120%. It will be overall compliant if the overall compliance rate is within 80-120%.

*Statistical Analysis Plan*

*SD-BS-014, version 1.0*

*Parent document: SOP-BS-005*

**Protocol code:** D-FR-10380-002

**Protocol Title:** A phase IIA, open-label, single-arm, two stage, multi-centre study to investigate the pharmacodynamics, pharmacokinetics, safety and tolerability of repeated subcutaneous administration of BIM23B065 in subjects with acromegaly

The descriptive statistics of the compliance percentages and rates on each day and overall will be presented.

A by-patient listing will be created to display the compliance on each day and overall along with the presentation of any specific action that was applied during the dosing and the description of the reason for dose administration not occurred as planned.

